Appendix 2. Visit Window Slotting Conventions

Visit Time Windows for Safety Analysis

Table 14 below presents the visits assigned for the safety analysis corresponding to the range of trial days (window) during which an actual visit may have occurred.

Table 14:	Visit Time	Windows	for	Safety	Analysis	
-----------	------------	---------	-----	--------	----------	--

Derived Visit	Scheduled Test / Visit Day ^a	Window
Baseline	Day 1	Days ≤1
Week 4 (Day 29) Visit	Day 29	Days [2, 43]
Week 8 (Day 57) Visit	Day 57	Days ≥44
End of Treatment ^b	End of Treatment Visit	

a. Relative to the day of randomization (Day 1)

b. "End of Treatment" will be presented in analysis tables for safety parameters, including ECG, clinical laboratory, and vital signs.

Test/Visit Day will be calculated as follows: test/visit date – date of randomization + 1.

If there are multiple values available for the same Visit, the data with the latest date for that visit will be utilized for summary.

Visit Time Windows for Efficacy Analysis

Table 15 presents the analysis weeks assigned for the efficacy analysis of the patient diary data related to daily GERD symptom assessment. These analysis weeks will be used in the calculations for all week-based parameters (eg, WHSS, WRFS, etc.).

Period	Analysis Week	Begins ^a	Ends ^a
Pretreatment	Week -2	Day -14	Day -8
(Baseline ^b)	Week -1	Day -7	Day -1 (Day before randomization) ^c
Treatment	Week 1	Day 1 (Day of Randomization) ^d	Day 7
	Week 2	Day 8	Day 14
	Week 3	Day 15	Day 21
	Week 4	Day 22	Day 28
	Week 5	Day 29	Day 35
	Week 6	Day 36	Day 42
	Week 7	Day 43	Day 49
	Week 8	Day 50	Day 56
	Week 9	Day 57	Day 63

 Table 15:
 Analysis Time Windows for Efficacy Analysis – Daily Assessments

a. Relative to the day of randomization (Day 1). There is no Day 0.

b. Baseline for efficacy parameters will be derived from the eDiary collected for Pretreatment Week -1 (Week -2 if data for Week -1 not available), specifically for the time dependent proportion parameters (defined as days with the event of interesting divided by the number of diary entry days during the relevant period) the last 14 days (Week -2 to Week -1) prior to day of randomization will be used.

- c. Day -1 for efficacy parameters derived from the morning diary.
- d. Day 1 for efficacy parameters derived from the morning diary.

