3.4.6 Selection and Timing of Dose for Each Patient

Patients will be randomized to receive 1500 mg IW-3718 BID or placebo BID. The first dose of study medication will be taken with liquid and a snack in clinic at the Randomization Visit (on Day 1). Patients should take their second dose that evening immediately upon completion of dinner, ensuring that at least 8 hours have elapsed since the first dose in clinic.

During the Treatment Period, patients will take study medication BID at home, in the morning (immediately upon completion of breakfast) and in the evening (immediately upon completion of dinner), even on study visit days. The last dose of study medication will be taken the morning of the EOT Visit.

Additionally, all patients will take their current PPI during the Pretreatment, Randomization, and Treatment Periods (ie, Day -21 through Day 57 [+ 3 days]). The PPI will be taken each day, approximately 30-60 minutes before breakfast.

During completion of the daily eDiary questions, patients will be asked to confirm daily dosing of their PPI by responding to the following question:

• "Did you take your PPI this morning?"

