7.4. Compliance

7.4.1. Treatment Compliance

Compliance with study drug dosing (IW-3718 or matching placebo) is defined as the total number of tablets taken by a patient during the study divided by the number of tablets that were expected to be taken, multiplied by 100. The total number of tablets taken will be calculated based on the following formula:

total number of tablets dispensed – (number of tablets returned + number of tablets lost)

The number of tablets lost is recorded on eCRF. The total number of tablets expected to be taken during the study equals the number of days in the study times 6 (minus 3 if the date ends on the day of EOT Visit).

The study drug compliance data will be reported using descriptive statistics for the Safety Population by treatment group. The compliance data will be categorized for increment of 20%, and it will be presented using patient counts and percentages for the Safety Population by treatment group. Additionally, compliance to PPI for the Pretreatment Period and for the Treatment Period will be summarized respectively similarly as the study drug.

7.4.2. eDiary Compliance

Patients are required to enter their diary assessments into the eDiary before bed each night, except assessment of sleep disturbance that is assessed upon getting up each morning during the Pretreatment and Treatment Periods. A daily report is considered complete if all questions in both the morning diary and evening diary (excluding the weekly assessments) are answered, with the following exceptions:

- For the first day of the Pretreatment Period, only the evening diary is expected.
- For the last day of the Pretreatment Period, only the morning diary will be used.
- For the first day of the Treatment Period, only the evening diary will be used.
- For the EOT Visit day, only the morning diary is expected.

eDiary compliance will be calculated for baseline (the Pretreatment Period), the Treatment Period, and weekly within the Treatment Period. For each period, eDiary compliance will be calculated as the number of completed daily reports divided by the expected number of daily reports in the period multiplied by 100.

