Appendix 6. Other Daily Assessments

Heartburn

The following question will be answered by the patient in the evening diary.

Over the past 24 hours, how would you rate the severity of your heartburn?

0=Did Not Have, 1=Very Mild, 2=Mild, 3=Moderate, 4=Moderately Severe, 5=Severe

Sleep Disturbance Due to GERD

The following questions will be answered by the patient upon getting up each morning (5:00 a.m. to 12:00 p.m.) using the eDiary:

Falling Asleep

Last night, did you have trouble falling asleep because of GERD symptoms?

[Yes, No]

Awakenings

Last night, how many times did you wake up during the night because of GERD symptoms?

0

1 time

2 times

3-5 times

6 or more times

Use of per-protocol rescue medicine (antacid)

How many times did you use your rescue medicine (liquid antacid) during the past 24 hours?

0

1 time

2 times

3-5 times

6 or more times

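### For the two sleep endpoints, SAP Table 15 counts the night before the first dose as treatment and leaves that night out of baseline

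*SAP*

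**What the plan says.** SAP Appendix 2, Table 15 sets the analysis weeks for daily diary data. Week -1 is Day -7 to Day -1, Week 1 is Day 1 to Day 7, Week 8 is Day 50 to Day 56, and the row after that is "Week 9 Day 57 Day 63". Two footnotes deal with the morning diary. Footnote c, on the end of Week -1, reads "Day -1 for efficacy parameters derived from the morning diary". Footnote d, on the start of Week 1, says the same for Day 1. Each repeats the day already printed in its cell.

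For proportion endpoints, SAP 7.9 and Table 15 footnote b take the 14 days before randomization as baseline, that is Day -14 to Day -1. Protocol Table 4 footnote b agrees. Protocol Table 4 has the same weekly windows and no morning-diary provision.

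The sleep items in SAP Appendix 6 are answered on getting up: "Last night, did you have trouble falling asleep because of GERD symptoms" and "Last night, how many times did you wake up during the night because of GERD symptoms". They feed exploratory endpoints 11 and 12 (SAP Table 7) and items 10 and 11 of the descriptive by-week list in SAP 7.9.3.

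On dosing, Protocol 3.4.6 states: "The first dose of study medication will be taken with liquid and a snack in clinic at the Randomization Visit". That is Day 1. It puts the last dose on the morning of the EOT Visit.

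SAP 7.4.2, on eDiary compliance, states: "For the first day of the Treatment Period, only the evening diary will be used". It adds: "For the EOT Visit day, only the morning diary is expected".

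**The concern.** A morning entry describes the night that ended that morning, so its treatment status depends on the day before. Table 15 applies evening-diary day boundaries to morning entries without an offset. The first treatment entry then describes a night before any study drug, and the last untreated night is missing from baseline.

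At stake is the accuracy of two exploratory endpoints and their by-week summaries. An untreated night counted as treated pulls any between-arm difference toward zero, most visibly in Week 1. The baseline proportion is also a covariate in the Poisson model, so the displaced night affects the adjustment as well. Finally, the compliance and efficacy calculations would assign the Day 1 morning diary differently.

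**Working it through.** The plan gives no figure to reproduce; the check is an enumeration of nights.

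**Inputs.** Recall is the previous night (SAP Appendix 6). The first dose is in clinic on Day 1 and the last on the morning of the EOT Visit (Protocol 3.4.6). The EOT Visit is Day 57 with a window of +3 days (Protocol 3.3.3). There is no Day 0 (Table 15 footnote a).

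**Rule.** The morning entry on Day d describes the night from the preceding day to Day d. A night is on treatment if it begins on or after Day 1 and ends by the morning of the last dose. The Day 1 entry covers the night from Day -1 to Day 1, which is pre-dose.

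**Eight-week window, EOT Visit on Day 57:**

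| Morning entries used | Entries | Pre-dose nights | On-treatment nights | Night of Day 56 |
|---|---|---|---|---|
| Day 1 to 56 (Table 15, Weeks 1 to 8) | 56 | 1 | 55 | out |
| Day 1 to 57 (if the period ends on Day 57) | 57 | 1 | 56 | in |
| Day 2 to 57 (shifted by one day) | 56 | 0 | 56 | in |

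**Share of pre-dose nights.** Week 1: 1/7 = 14.3%. Eight weeks: 1/56 = 1.8% (1/57 is also 1.8%).

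**Attenuation.** Assume complete diaries and the same between-arm difference on every treated night. Week 1 then shows 6/7 = 0.857 of that difference and the 8-week proportion 55/56 = 0.982.

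**Shift within one arm.** Let b be the pre-dose rate and t the on-treatment rate; both are assumed, since the documents give neither. The shift is (b - t)/56 over 8 weeks and (b - t)/7 in Week 1.
- b = 0.6, t = 0.3: 0.3/56 = 0.005 and 0.3/7 = 0.043.
- b = 0.8, t = 0.2: 0.6/56 = 0.011 and 0.6/7 = 0.086.

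**Baseline.** Mornings of Day -14 to Day -1 cover the nights ending on those days and omit the night ending on Day 1. In addition, SAP 7.4.2 expects only the evening diary on the first Pretreatment day. If Pretreatment starts on Day -14, no Day -14 morning entry is expected, and the 14-day window holds at most 13 nights. Mornings of Day -13 to Day 1 hold 14, all pre-dose.

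**Comparison with SAP 7.4.2.** It uses only the evening diary on the first treatment day, so the Day 1 morning entry is not a treatment entry there. With the morning diary expected on the EOT Visit day and an EOT Visit on Day 57, the treatment mornings are Day 2 to Day 57, the third row of the table.

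**Far end.** The Day 57 entry describes an on-treatment night and is eligible under Table 15 footnote e, because it falls on or before the last-dose day. Table 15 puts it in Week 9. With an EOT Visit between Day 57 and Day 60, Week 9 holds 1 to 4 on-treatment nights under Table 15 and 0 to 3 fall after Day 57 under the shifted window.

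**The case against.** The strongest case on the other side is that this hardly matters. Both endpoints are exploratory and outside multiplicity control, the by-week sleep summaries are descriptive, and one window rule applies to both blinded arms, so it cannot create a difference between them. That stands. The 6/7 factor also assumes an equal effect from the first treated night. Protocol 1.3 reports weekly numerical gains for heartburn severity in the Phase 2b study only from Week 2, so the documents do not support a material Week 1 difference to be diluted.

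A reader might infer that the last on-treatment night is lost from endpoints 11 and 12. The documents do not settle this. Those endpoints are proportions over the 8-week Treatment Period, which the heading of Protocol 3.6.2 runs to Day 57; Table 15 lists Week 9 under Treatment; and footnote e admits values up to the day of the last dose. On that reading the Day 57 entry is kept. Its absence is certain only for the Week 1 to Week 8 summaries.

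A reader might also take SAP 7.4.2 as a competing efficacy rule that overrides Table 15. It is not: it defines complete diary reports for compliance. It shows that the SAP handles the same entry in two ways, no more. That footnotes c and d were meant as an exception and were mis-entered is plausible, because they only repeat their cells, but it is an inference.

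None of this removes the pre-dose night from Week 1. Table 15 addresses the morning diary explicitly and puts that night under treatment on either reading of where the period ends.

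**Conclusion.** The window rule is wrong as written for morning-diary parameters. With complete diaries it places one pre-dose night in Week 1 for every patient, 1 of 7 nights there and about 1 of 56 over the period, and leaves the most recent untreated night out of baseline. This rests on the wording of the sleep items and the in-clinic first dose; the hour at which the Day 1 entry is made does not change the night it describes.

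The Day 57 entry is outside the by-week summaries. Whether it is outside endpoints 11 and 12 is an ambiguity to resolve, not an established loss. The effect is small, follows the same rule in both arms and tends to understate any difference. The primary and key secondary endpoints come from the evening diary and are unaffected, so nothing here bears on the trial's main conclusions.

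**What to change.** For morning-diary parameters only:
- Replace Table 15 footnotes c and d so that Week -1 ends with the Day 1 morning entry (Day -6 to Day 1), the 14-night baseline is Day -13 to Day 1, Week 1 starts with the Day 2 entry, and each later week moves by one day, making Week 8 Day 51 to Day 57.
- Add the same exception to SAP 7.9 and Table 15 footnote b. Both otherwise keep baseline strictly before the day of randomization and would contradict the new footnotes.
- Record the departure from Protocol Table 4 footnote b.
- State the last day that counts toward endpoints 11 and 12, and how on-treatment nights after Day 57 are handled when the EOT Visit is later. The shift alone does not settle those nights.

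Evening-diary windows stay as they are. The cost is these few wording changes and a one-day programming offset, with no new data and no effect on multiplicity. The change is best documented before unblinding.

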Appendix 3. Pooling of Trial Centers

Because of the potential of many study centers to have a small number of patients, the centers will be pooled by the following 6 geographic regions (as listed in Table 17): US Northeast, US Southeast, US Midwest, US Southwest, US West and Canada.

US Northeast	US Southeast	US Midwest	US Southwest	US West	Canada
СТ	AL	IA	AZ	CA	CANADA
DE	AR	IL	NM	CO	-
MA	FL	IN	OK	ID	-
MD	GA	KS	TX	MT	-
ME	KY	MI	-	NV	-
NH	LA	MN	-	OR	-
NJ	MS	MO	-	UT	-
NY	NC	ND	-	WA	-
PA	SC	NE	-	WY	-
RI	TN	OH	-	_	_
VT	VA	SD	-	_	_
-	WV	WI	-	_	_

 Table 17:
 Definition of Geographic Regions

Appendix 4. Schedule of Evaluations

Table 18:Schedule of Evaluations

	Screening Period (Up to 5 weeks)	Pretreatment Period (2 weeks)	Treatment Period (8 weeks)		Follow-up	
Visit Days →	Screening Visit (Day -56 to Day - 15)	Pretreatment Visit (Day -21 to Day - 1)	Randomization Visit (Day 1)	Week 4 Visit (Day 29 ± 3)	Week 8 / End- of-Treatment Visit (Day 57 + 3)	Safety Phone Call (EOT + 7d)
Visit Numbers →	Visit 1	Visit 2	Visit 3	Visit 4	Visit 5	
Study Procedure \downarrow						
Inclusion and Exclusion Criteria Verification	Х	X	Х			
Signing of ICF	Х					
IWRS Registration (a)	Х	X	Х	Х	Х	
Demographics	Х					
Medical & Disease History	Х					
Physical Examination (b)	Х				Х	
Body Weight and Height (c)	Х	X	Х	Х	Х	
H2RA/Antacid Washout (d)	Х					
EGD (e)	Х				Х	
Up to 96 Hours of pH Testing with Bravo Device (f)	Х					
Seated Vital Signs (g)	Х		X	Х	Х	
12-Lead ECG (h)	Х		Х		Х	
Prior and Concomitant Medications & Procedures (i)	Х	Х	Х	Х	Х	Х
Clinical Laboratory Tests (j)	Х		X	Х	Х	
Pregnancy Test (k)	Х		X	Х	Х	
Drug and Alcohol Screen (l)	Х					
AE Evaluations (m)	Х	X	X	Х	Х	Х
Rescue Medicine Dispensed (n)		X	X	Х		
eDiary Training and Dispensation		X				
eDiary (o)		X	Х	Х	Х	

	Screening Period (Up to 5 weeks)	Pretreatment Period (2 weeks)	т	reatment Perio (8 weeks)	od	Follow-up
Visit Days →	Screening Visit (Day -56 to Day - 15)	Pretreatment Visit (Day -21 to Day - 1)	Randomization Visit (Day 1)	Week 4 Visit (Day 29 ± 3)	Week 8 / End- of-Treatment Visit (Day 57 + 3)	Safety Phone Call (EOT + 7d)
Visit Numbers \rightarrow	Visit 1	Visit 2	Visit 3	Visit 4	Visit 5	
Study Procedure \downarrow						
Weekly Symptom and Treatment Assessments		Х	Х	Х	Х	
WPAI-Sleep-GERD			Х	Х	Х	
EQ-5D-3L			Х	Х	Х	
Randomization			Х			
Study Medication Dispensed (p)			Х	Х		
Study Medication Return (q)				Х	Х	
eDiary Return					Х	
Follow-up Phone Call (r)						Х

Abbreviations: AE = adverse event; BP = blood pressure; CBC = complete blood count; ECG = electrocardiogram; EGD = esophagogastroduodenoscopy; EOT = End-of-treatment; EQ = EuroQol; H2RA = histamine-2 receptor antagonist; HEENT = head, eyes, ears, nose, and throat; ICF = informed consent form; IWRS = interactive web response system; PPI = proton pump inhibitor; mRESQ-eD = modified Reflux Symptom Questionnaire Electronic Diary; SAE = serious adverse event

a. Site personnel will interact with IWRS to register the patient visit and transition the patient to the next appropriate study period.

b. A physical examination should include the following assessments: general appearance; HEENT; neck; cardiovascular; respiratory; abdomen/liver/spleen; musculoskeletal; lymph nodes; skin; neurologic; and mental status. Breast, genitourinary, and rectal examinations are optional and may be performed at the discretion of the Investigator.

c. Height will be measured only at the Screening Visit.

- d. During the Screening Period, patients will washout H2RAs at least 5 days prior, and antacids 1 day prior, to the EGD and Bravo testing. Patients may resume antacid use upon completion of the Bravo testing, but must refrain from H2RA use for the remainder of the study. During the Pretreatment Period, patients will refrain from using any anti-reflux medications, antacids, and H2RAs, except for the liquid antacid that is provided as rescue medication (aluminum hydroxide).
- e. All patients will be required to undergo an EGD during the Screening Period. There should be a minimum of 7 days between the EGD and the start of the Pretreatment Period to allow for pH testing and patient stabilization. A repeat EGD will be performed at the Week 8 / EOT Visit for all patients who have completed at least 4 weeks of treatment and had erosive esophagitis on the screening EGD (based on the Los Angeles [LA] classification of esophagitis, see Appendix 8) as determined by either the site personnel or the central reader.
- f. Up to 96 hours of pH testing with the Bravo device. If for some reason 96 hours of testing is not possible, then approximately 48 hours of testing is acceptable.

- g. Vital sign measurements include oral temperature (°C), respiratory rate, systolic and diastolic BP, and pulse. Respiratory rate, BP, and pulse measurements must be obtained after the patient has been seated for at least 5 minutes.
- h. 12-Lead ECGs should be obtained after the patient has been supine for at least 5 minutes.
- i. Prior medications will be collected at the Screening Visit as follows: all medicines taken by the patient during the 30 days before the Screening Visit, most recent use of PPIs, H2RAs, and antacids. Concomitant medications and procedures will be collected in the EDC system.
- j. Clinical laboratory tests include clinical chemistry, hematology (CBC), coagulation, and urinalysis. If the triglyceride value exceeds the protocol-specified criteria and the patient was not under fasted conditions, the patient may return to complete a fasted lipid panel.
- k. For all female patients of childbearing potential, a negative urine or serum pregnancy test must be performed and documented at the Screening Visit, and at the Randomization Visit (before dosing) in order for the patient to be randomized into the study. A urine or serum pregnancy test will also be obtained at the Week 4 and EOT Visits. All positive urine pregnancy test results will be confirmed by a serum pregnancy test.
- 1. Patients must undergo a urine drug screen for selected drugs of abuse (cocaine, barbiturates, amphetamines, opiates, benzodiazepines, and cannabinoids) and a serum alcohol screen at the Screening Visit.
- m. For randomized patients, all AEs will be captured from the time the patient signs the ICF through the Follow-up Phone call.
- n. Rescue medicine (aluminum hydroxide / magnesium hydroxide) will be supplied to patients at the Pretreatment Visit, and if needed, at subsequent visits.
- o. The eDiary will be dispensed at the Pretreatment Visit. Patients must complete daily questions at least 5 days each week during the 14 days before the Treatment Period and must complete the weekly questions at least once during the 7 days before the Treatment Period in order to be eligible for randomization. Patients should bring their eDiary to each visit. The eDiary will be used for daily assessments (PPI administration, mRESQ-eD, dyspepsia symptoms, sleep disturbance, and rescue medication use), and weekly assessments (degree of relief, symptom bothersomeness, symptom relief, treatment satisfaction, and questionnaires).
- p. The first dose of study medication will be administered in the clinic with liquid and a snack at the Randomization Visit. At all other visits, patients will take study medication prior to arriving at the clinic but will be dispensed additional doses needed until the next study visit.
- q. Treatment adherence with study drug will be assessed based on return of unused tablets.
- r. Study site will contact each patient via telephone 7 days after the EOT Visit to collect information pertaining to ongoing AEs/SAEs/concomitant medications/concomitant therapies, and information concerning any new AEs/SAEs /concomitant medications/concomitant therapies since the EOT Visit.

Appendix 5.Modified Reflux Symptom Questionnaire Electronic Diary

Instructions: Please answer the following questions to help us understand the symptoms you experienced over the past 24 hours because of your reflux disease. For each question, please choose the answer most appropriate for you.

1.	Over the past 24 hours, how would you rate the severity of your burning feeling behind the breastbone or in the center of the upper stomach?
	0=Did not have/ 1=Very mild/ 2=Mild/ 3=Moderate/ 4=Moderately severe/ 5=Severe
2.	Over the past 24 hours, how would you rate the severity of your pain behind the breastbone or in the center of the upper stomach?
	0=Did not have/ 1=Very mild/ 2=Mild/ 3=Moderate/ 4=Moderately severe/ 5=Severe
3.	Over the past 24 hours, how would you rate the severity of your difficulty swallowing?
	0=Did not have/1=Very mild/2=Mild/3=Moderate/4=Moderately severe/5=Severe
4.	Over the past 24 hours, how would you rate the severity of your hoarseness?
	0=Did not have/ 1=Very mild/ 2=Mild/ 3=Moderate/ 4=Moderately severe/ 5=Severe
5.	Over the past 24 hours, how would you rate the severity of your cough?
	0=Did not have/ 1=Very mild/ 2=Mild/ 3=Moderate/ 4=Moderately severe/ 5=Severe
6.	Over the past 24 hours, how often did you experience regurgitation (liquid or food moving upwards towards your throat or mouth)?
	0=Never/1=Rarely/2=Sometimes/3=Often/4=Very often
7.	Over the past 24 hours, how often did you experience an acid or bitter taste in the mouth?
	0=Never/1-Rarely/2=Sometimes/3=Often/4=Very often
8.	Over the past 24 hours, how often did you experience burping?
	0=Never/1=Rarely/2=Sometimes/3=Often/4=Very often

